3.2. Inclusion and Exclusion Criteria

Participant inclusion and exclusion criteria are listed in Table 4.

Table 4. Inclusion and Exclusion Criteria

	Physicians	Patients	Caregivers	Research Coordinator	Patient Coach	Physician Coach
Inclusion Criteria	
1. Member of Strong nephrology group working at Strong Memorial Hospital, Highland Hospital, FF Thompson or Rochester General Hospital
 
2. Treat patients with CKD
	
1. Age ≥ 65 years old
 
2. Presence of advanced CKD stage 4 or 5 (i.e. GFR, eGFR, or GFR by Cystatin ≤ 25 ml/min)
 
3. Patient's nephrologist is enrolled in the study and has seen that nephrologist at least once
 
4. Speaks English
 
5. Have not attended a dialysis education class or met with the dialysis education coordinator within 2 years prior to the study start date.
 
6. Have not made a dialysis decision
	
Consenting patients will be asked for permission to contact up to three caregivers, defined as a "family member, partner, friend or someone else who is involved with their health care issues, for example, someone whom they talk to about personal issues including medical decisions or who comes to doctor appointments with them. This person may also help with routine day-to-day activities, like transportation or paperwork." The term "caregiver" is used here for scientific purposes only; it is not essential that this individual self-identify as a caregiver.
 
1. Self-identified caregiver (per the definition above)
 
2. 21 years of age or older.
	
1. Assisted in the study by recruiting, consenting, and interviewing at least one subject.
	
1. Assisted in the study by completing at least one coaching session with a subject.
	
1. Assisted in the study by completing at least one coaching session with a nephrologist

Exclusion Criteria	
1. Expecting to leave in six months.
	
1. Patient has already been seen by a palliative care clinician or is enrolled in hospice
 
2. Is already on dialysis
 
3. Hospitalized at the time of recruitment
 
4. Cognitive impairment and no legally authorized representative is available
	
4. Support is offered primarily in a professional role (e.g., clergy).
 
5. Cognitive impairment
	
6. Did not recruit, consent, or interview any patients.
	
7. Did not complete any coaching sessions with patients.
	
8. Did not complete any coaching sessions with nephrologists.

---------------------------	--	--	--	---	--	---

		5. Anyone needing a language interpreter (including sign language)	
--	--	--	--

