Interested subjects will then be contacted for screening as described in this protocol. Subjects who are not interested will not be contacted and will be removed from the pool of eligible subjects. If subjects do not indicate whether or not they are interested in participating, they may be re-sent the email notification one additional time, no sooner than one week after the first email was sent. When study accrual has been completed, outstanding research opportunities in MyChart will be rescinded.

Also, patients from Rochester General will only be approached if their participating nephrologist has discussed the study with them first, they are aware of what the study is about and they are agreeable to speaking with the RA. This will be done either in person or by telephone depending on the patient's preference.

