5. METHODS AND STUDY PROCEDURES

5.1. Overview of the Procedures

After a **nephrologist** has consented for the study, he/she will be asked to complete a study entry questionnaire. It should require no more than 15 minutes to complete the questionnaire (**Table 5**).

Randomization: After enrollment and baseline data are obtained, nephrologists will be randomized to either the intervention or control group of the study by study personnel who will be blinded to their identities. This is a cluster RCT. Thus, patients of nephrologists in the intervention group will be assigned to the intervention group; patients of nephrologists in the control group will be assigned to the control group.

After a **patient coach** has completed all coaching sessions and follow up calls with their assigned subjects they will be asked to participate in a qualitative interview.

After a **physician coach** has completed all coaching sessions and follow up correspondence with nephrologists enrolled in the intervention arm they will be asked to participate in a qualitative interview.

At study completion all assisting **research coordinators** will be asked to participate in a qualitative interview.

Intervention:

Nephrologist component: We will conduct a pre-research focus group or individual sessions for nephrologists to learn about the skills and barriers that will help them become better communicators for shared dialysis decision-making. Nephrologists in the intervention group may be provided with supplies such as a notebook, pen and highlighter. They will then participate in a brief value affirmation exercise and goals of communication training at the time of enrollment and completion of their baseline assessments. Nephrologists will receive links to watch 5 communication training videos and then partake in up to three Zoom educational sessions, each approximately 45-60 minutes in duration, approximately 1-3 weeks apart, with standardized patient instructors (SPI) who will be enacting roles of patients with advanced kidney disease. The SPI will provide immediate oral feedback to the nephrologist. The specific communication behaviors that will be targeted include: (1) engagement, by acknowledging and prioritizing patient concerns (2) empathy (3) ASK-TELL-ASK approach (4) decision-making skills:

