(a) value/preference clarification (b) compare options including conservative management (c) choose an option that seems to best fit with patient preferences. An effort will be made to tailor these sessions to the individual needs of a nephrologist by reviewing the identified needs and discussion with the coach. The communication coaching session will be audio-recorded, and nephrologists will receive written feedback via email following the sessions to reinforce their

learning. A manual and fidelity checklist will be developed to deliver this component of the intervention.

Patient recruitment at Strong, Highland and Rochester General Hospital will start once a nephrologist in the intervention group has completed at least two communication coaching sessions. At the end of each patient visit, nephrologists will be asked if (a) a preliminary RRT decision has been made? If not, is there a plan to discuss it in the next visit? Once a patient has made an RRT decision or has seen the nephrologist twice, either in-person or via Zoom, a final set of assessments will be completed. At the end of the study, to check for contamination, nephrologists in the intervention group will be asked if they were able to share newly learned communication skills with the nephrologists in the control group.

Upon completion of the decision-making process with the nephrologist, depending on patient's choice, patients will be given a summary of the 'next steps,' prepared in conjunction with the treating nephrologist. A copy will be given to the patient by the research coordinator in-person or via mail: (1) When does the patient need to finalize the decision (only if the decision has not been made after two visits)? (2) At what GFR level, access will be placed? (3) Symptoms suggestive of need for dialysis (4) when will dialysis need to be initiated?

Patient component (and caregivers, if available):

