Control Group Nephrologists: will receive no educational intervention and will deliver care to control patients using routine communication processes during the study period. After appointments with patients enrolled in the study, physicians in the control group will also be asked if (a) a preliminary RRT decision has been made? Once a patient has made an RRT decision or has seen the nephrologist twice, either in-person or via Zoom, a final set of assessments will be completed. Upon completion of their final qualitative interview, they will have access to communication videos and an opportunity to participate in a workshop to improve communication skills where nephrologists may be provided with supplies such as a notebook, pen and highlighter. However, up to two visits with their patients will be audio-recorded. Audio recordings will be destroyed after transcription and analyzation is complete. At the end of the study, to check for contamination, nephrologists in the control group, will be asked if they were able to learn new communication skills from the nephrologists in the intervention group.

Patients (and caregivers, if available): During recruitment periods, a research assistant will identify eligible patients by reviewing the clinic schedule at Strong, Highland Hospital, and FF Thompson (patients who meet the eligibility requirements at RGH will be identified by the RGH PI) to include all current patients who meet eligibility criteria. Patients will be introduced to the study in-person at the study site location or over the phone and asked by the research assistant if they are willing to speak in a private setting to learn more about the study. All patients will be told that the purpose of the study is to improve communication and decision-making between patients and nephrologists. Patients will be given time to think about participation, and if desired will be told how to contact the research assistant at a later time. The screening and consent process will continue as long as needed until the person obtaining consent is

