	Decisional engagement scale	Hoerger et al, Psychol Assess. 2016	10	0-3 months 3-6 months at Study completion

	Choice of renal replacement therapy modality	NA	1	Study entry 0-3 months 3-6 months at Study completion
	Prognostic discussion	Weeks et al, JAMA 1998	10	Study entry 0-3 months 3-6 months at Study completion
	Decisional Conflict scale	Med Decis Making. 1995	10	Study entry 0-3 months 3-6 months at Study completion
	Goal Concordant Care Questionnaire	Curtis et al	2	Study entry 0-3 months 3-6 months at Study completion
Other potential co-variates	Demographics	NA	17	Study entry
	Cavanaugh dialysis knowledge scale – Rochester version	Cavanaugh et al, CJASN 2009	14	Study entry 0-3 months 3-6 months at Study completion
	Human connection scale	Mack et al Cancer 2009	16	Study entry 0-3 months
	Healthcare climate questionnaire	XX	5	Study entry 0-3 months
	Quality of life (KDQOL)		32	Study entry 0-3 months 3-6 months at Study completion
	Control preference scale- Rochester version	Degner et al, Can J Nurs Res. 1990	1	Study entry
	Health literacy	Davis et al, family medicine, 1991	6	Study entry
	Trust - Primary Care Assessment Survey (PCAS) trust subscale	Safran DG, Kosinski M, Tarlov AR, Med Care. 1998;	8	Study entry 0-3 months 3-6 months at Study completion
	KARNOFSKY SELF-REPORTED PERFORMANCE	Crooks at al. J Gerontol. 1991;	1	Study entry 3-6 months at Study completion
	OARS Comorbidity	Fillenbaum et al. J Gerontol. 1981;	15	Study entry
	Press Ganey Patient Satisfaction Questionnaire	NA	16	Study entry 0-3 months
	Perceived Efficacy in Patient-Physician Interactions	JAGS, April 2015	5	Study entry 0-3 months 3-6 months at Study completion

	Advanced care planning	NA	4	Study entry 3-6 months at Study completion
--	------------------------	----	---	--

	Hospitalizations	NA	2	Study entry 0-3 months 3-6 months at Study completion
	Exit interview	NA	3	Upon withdrawal

Table 7. Assessments and timing of administration of assessments for caregivers

	Assessment	References if applicable	# of items	Time of completion
Aim-1	Feasibility (patients approached vs enrolled)	Weiner et al, Implement Science, 2017	Feasibility of the intervention measure	0-3 months (after last coaching session)
			Feasibility of the Question Prompt List	
			Feasibility of the Education Booklet	
			Feasibility of Education video	
	Acceptability	NA	Qualitative interviews	0-3 months (after last coaching session)

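### Patients are screened after their nephrologist is randomized (and, in the intervention arm, coached) with no check on visits in between, so the no-decision criterion may select differently by arm and study-entry scores cannot be assumed pre-intervention

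*Combined protocol and SAP*

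**What the plan says.** The order of events comes from several places in the combined protocol and SAP.

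- **Randomization (section 5.1).** "After enrollment and baseline data are obtained, nephrologists will be randomized to either the intervention or control group". The baseline data meant here are the nephrologist's own. No step places patient identification before this point.
- **Recruitment start, intervention arm (section 5.1, nephrologist component).** Recruitment at Strong, Highland and Rochester General "will start once a nephrologist in the intervention group has completed at least two communication coaching sessions". FF Thompson is not named in that sentence.
- **Control arm (section 5.1).** Control nephrologists "will receive no educational intervention and will deliver care to control patients using routine communication processes during the study period". No start date or lag is given for recruiting their patients.
- **Eligibility (section 3.2, Table 4).** Criterion 3 requires that the patient's "nephrologist is enrolled in the study and has seen that nephrologist at least once", with no date limit relative to training. Criterion 6 is "Have not made a dialysis decision".
- **Approach (sections 4.1 and 5.1).** The research assistant works from clinic schedules and may approach patients in clinic, by phone, by email or through MyChart. In addition, "patients from Rochester General will only be approached if their participating nephrologist has discussed the study with them first", although section 4.2 also lets that site's study PI hold the initial discussion.
- **Assessments (Table 6).** Prognostic discussion, decisional conflict, goal-concordant care and treatment choice are scheduled at "Study entry 0-3 months 3-6 months at Study completion". APPC, OPTION, the SDM questionnaire and the decisional engagement scale have no study-entry measurement.
- **Analysis (section 11.1).** The models carry physician-level covariates and patient demographics. They contain no study-entry outcome score and no term for visits before entry.

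**The concern.** In a cluster trial where patients join after allocation, eligibility must not depend on anything that allocation can change. Whether a patient has already reached a dialysis decision is such a variable. The coaching targets decision-making skills, including clarifying values, comparing options and choosing one. If trained nephrologists bring patients to a decision at a different rate in ordinary visits before the research assistant makes contact, criterion 6 removes a different kind of patient in each arm. That could shift every Aim 2 patient outcome, including those coded from recordings.

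The second issue is the meaning of study entry. An intervention patient who has seen the trained nephrologist before enrolling has already received part of DIAL-SDM when the entry questionnaires are completed. A control patient in the same position has not.

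Aim 2 exists to produce effect sizes for a larger cluster trial (sections 1.1, 2.2 and 3.1), so a distortion here would carry into that trial's design.

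**Working it through.** The plan gives no figure on this point. Its one calculation, the power statement for OPTION in section 3.1, does not depend on the order of recruitment. The check is therefore a reading of the sequence, followed by an illustration on assumed rates.

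**1. Can a trained visit precede enrolment?** Yes, and the workflow makes it plausible. Consent covers recording of future visits. An intervention patient receives booklets about 2–4 weeks before coaching, and coaching falls within two weeks before the nephrology visit (section 5.1). The gap from booklet to study visit is therefore about 2 + 0 = 2 to 4 + 2 = 6 weeks. For a patient approached at a clinic visit, that visit cannot ordinarily be the recorded one, and nothing says whether the entry survey comes before it. The study period, August 2021 to September 2025, leaves room for further visits.

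**2. Is there a safeguard?** None was found. Section 4.2 records numbers approached, enrolled and declined, with reasons, and keeps screening data for patients found ineligible after approach. Section 4.1 records nephrologists' reasons for refusal. Neither covers patients removed at record review because they decided after training, nor counts visits since training.

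**3. Selection under criterion 6.** All rates here are assumptions. Let q be the share of otherwise eligible patients with one visit between training and screening (or the same period for controls), equal in both arms. Let p be the probability that such a visit ends in a decision. The share removed is q × p.

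| q | p usual / trained | Control removed | Intervention removed | Gap (points) |
|---|---|---|---|---|
| 0.25 | 0.10 / 0.20 | 2.5% | 5.0% | 2.5 |
| 0.25 | 0.10 / 0.30 | 2.5% | 7.5% | 5.0 |
| 0.25 | 0.20 / 0.50 | 5.0% | 12.5% | 7.5 |
| 0.50 | 0.10 / 0.20 | 5.0% | 10.0% | 5.0 |
| 0.50 | 0.10 / 0.30 | 5.0% | 15.0% | 10.0 |
| 0.50 | 0.20 / 0.50 | 10.0% | 25.0% | 15.0 |
| 0.75 | 0.10 / 0.20 | 7.5% | 15.0% | 7.5 |
| 0.75 | 0.10 / 0.30 | 7.5% | 22.5% | 15.0 |
| 0.75 | 0.20 / 0.50 | 15.0% | 37.5% | 22.5 |

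**4. Effect on case mix.** Suppose half the candidates decide readily (rate 1.5p) and half reluctantly (rate 0.5p). The ready share among those left is (1 − 1.5qp) / [2(1 − qp)]. Across the table this is 46–49% in control and 35–49% in intervention. The extreme intervention case is (1 − 0.5625) / (2 × 0.625) = 0.35.

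**5. Direction.** If training lengthened deliberation instead, the imbalance would reverse. With q = 0.50, p = 0.20 usual and p = 0.10 trained, 10% of control and 5% of intervention candidates would be removed.

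**6. Entry scores.** If a share q of intervention patients already shows a fraction f of the effect at entry, a change-from-entry analysis loses q × f of it: 0.25 × 0.25 = 6% up to 0.75 × 0.5 = 37.5%. This applies only to outcomes with an entry score, and only if change from entry is analysed.

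**The case against.** Training clinicians before recruiting their patients is inherent in this intervention. Aim 1 is primary and mainly descriptive, and Aim 2 is preliminary. Both statements are fair. They limit the priority of the point but do not remove it, because the Aim 2 effect sizes are intended for use in the next trial.

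A reader might infer several stronger things that the documents do not support.

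- **That entry scores in the intervention arm are contaminated.** For a patient not seen since training they are in effect pre-intervention, and for all patients they precede the coaching session, role-play and question list. The text supports only that they cannot be assumed clean.
- **That baseline adjustment removes a set share of the effect.** With an entry-to-follow-up correlation of 0.5 and half the effect present at entry, adjustment would remove 0.5 × 0.5 = 25%. But section 11.1 plans no such adjustment and no change score, and both inputs are assumed. The powered outcome, OPTION, has no entry score.
- **That criterion 6 screens on an Aim 2 outcome.** Aim 2(c) concerns which option is chosen, not whether or how soon one is.
- **That effects are biased toward zero.** No passage says that training speeds decisions, and undecided patients are offered further coaching. Patients who remain undecided might also have fuller recorded discussions.
- **That the bias is undetectable.** Nephrology visits are documented in both arms to clinical standards (section 4.2) and staff will have access to records, so prior visit dates should be recoverable. They are simply not planned to be used.

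**Conclusion.** The point holds in limited form. Eligibility is judged after randomization and, for intervention nephrologists at the three named sites, after at least two coaching sessions. It uses a variable that training may change, with no matching index date for controls and no record of visits in between. Differential selection could affect all Aim 2 patient outcomes. Doubt about the baseline is confined to outcomes measured at entry: prognostic discussion, decisional conflict, goal-concordant care and treatment choice.

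The documents give no visit interval, accrual pattern or decision rate, so neither size nor sign can be computed from them. The 2.5–15% (control) and 5–37.5% (intervention) exclusion figures assume that training raises the chance of a decision and that interim visits are equally common in both arms. They show that the problem could range from minor to material and are not an estimate. It should be corrected or at least made visible, because the remedy is cheap.

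**What to change.** 1. **Dated list.** In both arms, run the record query at the nephrologist's randomization date, before any training. Save the list of patients who appear to meet the criteria that the record can show, confirm the rest at approach, and approach from this list first. Confirmation is needed because usual-care dialysis education is routinely not in the record (section 4.2), so criterion 5 cannot be settled by query alone.
2. **Screening log.** For every patient screened, including those removed at record review, log visits to that nephrologist since randomization and any exclusion for a decision made since then. Report both by arm.
3. **Section 11.1.** Define an index date: completion of the second coaching session, or the same calendar lag after randomization for controls. Treat a study-entry score as a baseline, for any change score or adjustment, only if the patient had no visit to that nephrologist between the index date and entry. Add a sensitivity analysis of Aim 2 outcomes restricted to patients with no such visit.

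Do not require the first post-training visit to be the study visit. The booklet and coaching lead times in section 5.1 would rule this out for patients seen soon after training.

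The cost is one query per nephrologist, two log fields and a short SAP addition. The dated list may be short for some nephrologists, so later patients would still be enrolled but flagged. With 60 patients in total, the restricted analysis will be small.

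If enrolment is finished, only the reporting and the sensitivity analysis apply, with prior visit dates sought from the medical records. The abstraction planned in section 5.2 covers 6 months before entry and does not name nephrology visits, so it may need to be extended back to the randomization date.

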4. SUBJECT IDENTIFICATION, RECRUITMENT AND CONSENT

4.1. Method of Subject Identification and Recruitment

A Study personnel (PI or the RA) will provide an overview of the study to the nephrologists as a group, or meet with nephrologists in person or via Zoom to brief them on study procedures including physician measures (Table 5).

The PI will provide an overview of the study to the Research Coordinators as a group, or individually via Zoom or in person.

A study personnel (PI or the RA) will provide an overview of the study to the patient coaches and physician coaches as a group, or individually via Zoom or in person.

Based on the inclusion and exclusion criteria, the PI or RA will screen nephrology clinic patients at Strong, Highland, and FF Thompson for study eligibility using e-record and at Rochester General Hospital through RGH's PI screening. The study team will communicate with the participating nephrologist's in-person, via telephone, or by email if they have questions about the eligibility of a patient or need more information. This process is implemented to eliminate patients with favorable renal prognosis who are less likely to need dialysis in the future. The assumption is that participating nephrologists will permit all their patients to be approached, and this will be stated in the nephrologist consent form. However, nephrologists' can decline patient participation in the study if a patient is unlikely to progress to needing dialysis. Data on nephrologists' reasons for refusal and referral will be captured on a separate sheet.

After acquiring consent from the nephrologists, The RA will approach eligible patients (and caregivers, if present) either in person in the clinic, by calling them on the phone, emailing them, or sending them a message via MyChart. If through MyChart, eligible subjects will receive an email or text notifying them that they have a new research opportunity available in MyChart. It can only be viewed after they log in to MyChart and visit the Research Studies page. Subjects will see a description of the study, which is included on the attached MyChart for Recruitment Request form (uploaded as part of recruitment materials). Underneath the study description on the Research Studies page, subjects will indicate whether or not they are interested in participating by clicking on the corresponding button. This will trigger a notification that is sent to the study coordinator's Inbasket in eRecord.

Interested subjects will then be contacted for screening as described in this protocol. Subjects who are not interested will not be contacted and will be removed from the pool of eligible subjects. If subjects do not indicate whether or not they are interested in participating, they may be re-sent the email notification one additional time, no sooner than one week after the first email was sent. When study accrual has been completed, outstanding research opportunities in MyChart will be rescinded.

Also, patients from Rochester General will only be approached if their participating nephrologist has discussed the study with them first, they are aware of what the study is about and they are agreeable to speaking with the RA. This will be done either in person or by telephone depending on the patient's preference.

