For patients who fail this screen or if the RA has additional concerns, we will require that their guardian participate in the consenting process and sign an informed consent. We will also require that patients still give consent, or at minimum assent if fully informed consent is not possible. For such patients, a legally authorized representative (LAR) will fill out the assessments and participate in coaching sessions, if assigned to the intervention group. In this study, the LAR will typically be, in order of priority: someone who is a healthcare agent by advance directive, or a healthcare surrogate decision maker by local law such as a spouse, adult child, or sibling. We are choosing to keep patients with limited capacity in our pilot as these patients may still be able to provide appropriate responses about their wishes etc. We will exclude the caregivers lacking capacity to consent for the study.

We will keep a record of the number of eligible physicians, patients and caregivers approached for potential enrollment as well as the number enrolled and declined. Reasons for refusal will be documented on a separate sheet. Patients deemed not to be eligible after approaching them will be informed about the lack of eligibility and their screening data will be maintained.

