comfortable that the prospective participant fully understands all aspects of study involvement. The research assistant will obtain written consent or eConsent from those who voluntarily choose to enroll, using approved consent forms. All patients (and caregivers, if available) will be asked to allow audio-recording of 1-2 future visits with their nephrologist depending on the status of dialysis decision-making, and for permission to participate in three sets of surveys, collection of demographic data, and the end-of-study interview, and exit interview for those who withdraw early from the study. We expect that most of the patients will need one in-person visit with a coach and one in-person visit with the nephrologist. We will keep a record of this data. For patients not able to make a decision after one visit (as assessed during the coach's phone call after the nephrologist's visit), an additional in-person coaching visit will be offered. For such patients, the follow-up nephrology visits will also be audio-recorded. Patients will be able to participate in these sessions via zoom or in-person.

Patients will be informed that this is a randomized study, and their own study assignment will depend on which assignment their nephrologist has received. They will be informed about the multiple phases of the study and that their total involvement will take about 60-90 minutes for each coaching session, approximately 30 minutes to complete each survey set, approximately 15 minutes for each phone call from a coach, and approximately 30 minutes for an interview about the feasibility/acceptability of the study, approximately 5 minutes for an exit interview for those who withdraw early, till the end of the study. Patients will be asked for written permission to (a) Audio-record visits with their nephrologist and coaches (b) Complete surveys at study entry, within 0-3 months after visit(s) with their nephrologist, and within 3-6 months at study completion (c) Allow research staff to access their medical records (d) Participate in the end-of-study interview (d) participate in an exit interview upon study withdraw.

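### Nephrologists who in effect know their arm can decline patients on an unspecified prognosis judgement, and the planned models adjust for no measure of kidney disease severity

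*Combined protocol and SAP*

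**What the plan says.** **Order of events.** Section 5.1: "After enrollment and baseline data are obtained, nephrologists will be randomized to either the intervention or control group". Patient recruitment at Strong, Highland and Rochester General "will start once a nephrologist in the intervention group has completed at least two communication coaching sessions". Control nephrologists receive no training during the study period. Patients are told that "their own study assignment will depend on which assignment their nephrologist has received".

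**The veto.** Section 4.1 says nephrologists "can decline patient participation in the study if a patient is unlikely to progress to needing dialysis". No eGFR slope, risk-score cut-off or masked adjudication goes with it. The stated purpose of the check is to leave out patients with a favourable renal outlook.

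**First contact at Rochester General.** Section 4.1 says patients there "will only be approached if their participating nephrologist has discussed the study with them first". Section 4.2 instead allows the initial discussion to be held by either the nephrologist or that site's study PI.

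**Safeguards.** Table 4 sets a GFR limit of 25 ml/min or less. Section 4.1 states a default, to be written into the nephrologist consent form: "The assumption is that participating nephrologists will permit all their patients to be approached". The nephrologists' "reasons for refusal and referral will be captured on a separate sheet". Section 4.2 adds: "We will keep a record of the number of eligible physicians, patients and caregivers approached for potential enrollment", along with numbers enrolled and declined.

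**Analysis.** Section 11.1 lists five physician-level covariates. At patient level it names demographic characteristics only. No comparison of vetoes or approach rates by arm is planned.

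**The concern.** Randomising nephrologists balances nephrologists in expectation. It does not balance patients whom those nephrologists help to select once the arm is known. The ground for the veto is likelihood of progression, which could plausibly be related to how fully dialysis is discussed and to what the patient chooses. If the two arms apply the undefined ground differently, the patients compared under Aim 2 differ at baseline in a variable the model does not contain.

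The study is a pilot, but section 11.1 tests group differences at a two-sided 5% level, and sections 2.2 and 3.1 look ahead to a larger cluster trial that will use these effect sizes. A case-mix difference would pass into that trial's planning, and the same recruitment route could be repeated there.

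**Working it through.** **Step 1. Does the veto fall after allocation, by someone who knows the arm?** Section 5.1 puts randomisation before coaching, and coaching before patient recruitment. For control patients, the wording on inherited assignment implies the same order. No sentence says that nephrologists are told their arm; it follows from having been coached or not. Section 11.2 also reports the allocated arm of one monitoring board member, which fits open allocation. The only masking described in section 5.1 is of the staff who perform the randomisation, to the nephrologists' identities.

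**Step 2. Do the safeguards close the gap?**

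| Safeguard | What it does | What it leaves open |
|---|---|---|
| GFR limit (Table 4) | Bounds severity objectively | Progression risk below the limit |
| Default that all may be approached (4.1) | Should keep vetoes few | The veto is granted as an exception |
| Refusal and approach logs (4.1, 4.2) | Records what happened | No comparison by arm planned |
| Covariates (11.1) | Adjusts for demographics | No eGFR or risk score named |

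**Step 3. The plan's own precision.** Inputs from section 3.1: 60 patients, about 5 per nephrologist, SD 11, ICC 0.1, cluster-size CV 0.5. Assumed: 30 patients per arm and 12 clusters (60/5; section 9.1 also gives about 12).

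- Design effect = 1 + ((1 + CV²)m − 1) × ICC = 1 + (1.25 × 5 − 1) × 0.1 = 1.525
- Effective n per arm = 30/1.525 = 19.7
- SE of the difference = 11 × √(2/19.67) = 3.51 OPTION points

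Section 3.1 states 80% power for 15 points. These inputs give 99.0% (normal) or 97.0% (t, 10 df), so the stated figure does not reproduce and is conservative. The present point uses only the SE and does not rest on that power figure.

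**Step 4. Illustration of a selection shift.** The documents give no veto rate and no link between prognosis and OPTION score, so the shift b is an assumption. With no true effect, the two-sided error is Φ(b/SE − 1.96) + Φ(−b/SE − 1.96).

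| Assumed b (points) | b/SE | Error, normal | Error, t (10 df) |
|---|---|---|---|
| 1 | 0.285 | 0.0470 + 0.0124 = 5.9% | 5.8% |
| 2 | 0.570 | 0.0823 + 0.0057 = 8.8% | 8.1% |
| 3 | 0.855 | 0.1347 + 0.0024 = 13.7% | 12.1% |

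The documents give the number of nephrologists as 10 (Table 1), about 12 (section 9.1) and up to 16 (section 3.1). With 10 clusters (m = 6, SE 3.65), shifts of 1 and 3 points give 5.9% and 13.0%; with 16 (m = 3.75, SE 3.32), 6.0% and 14.7%. The result hardly depends on this choice.

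**The case against.** The case on the other side has weight. Study staff screen from the record against an objective GFR limit, the veto has a single ground, and permitting everyone is the default. All patients are told the same study purpose, and the research assistant obtains consent. The coaching targets engagement, empathy and decision-making skills, not estimation of progression, so a training effect on the veto is conjecture. Table 6 collects comorbidity, performance status and quality of life at entry as potential covariates, and section 5.2 abstracts laboratory values, so severity data exist. A shift of 1 to 3 points is less than one standard error and far below the 15-point design difference. The primary aim is feasibility, acceptability and fidelity.

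Most of this stands and limits the point. It does not answer it: collecting potential covariates is not the same as committing to one, and logging vetoes is not the same as comparing them.

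A reader might infer more than the documents support:

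- **That coached nephrologists will veto differently, in a known direction.** Nothing in the documents shows this.
- **That Rochester General nephrologists must always introduce the study.** Section 4.1 read alone says so, but section 4.2 allows the site's study PI to do it. The two passages conflict.
- **That treatment choice could shift by as much as the case mix does.** That needs low-risk and high-risk patients to make completely opposite choices.
- **That a new masked eligibility rule is a simple amendment.** It would need masked screening staff, Rochester General screens through its own PI, and the stated study window of August 2021 to September 2025 suggests much of recruitment may be over.

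**Conclusion.** The point holds in a limited form. The documented sequence lets nephrologists who in effect know their arm exclude patients on an undefined prognosis judgement, and the analysis neither adjusts for kidney disease severity nor compares exclusions by arm. The arms can therefore differ in baseline progression risk; whether they do, in which direction and by how much cannot be told from the documents.

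The 6% to 14% error range is an illustration. It rests on an assumed shift of 1 to 3 OPTION points, 12 clusters of 5, equal arms and the section 3.1 SD, ICC and CV. It concerns the comparisons in Aims 2 and 3 and the effect sizes carried forward. The acceptability and fidelity results are little affected. The change is worth making because the parts that matter cost almost nothing.

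**What to change.** 1. In section 11.1, pre-specify baseline eGFR as a patient-level covariate in the Aim 2 models and any Aim 3 models. The kidney-failure risk score from the model already cited in section 5.1 could be used instead where its inputs are in the record. A GFR value is already needed for eligibility. Adjustment reduces imbalance in what is measured; it cannot remove selection on a nephrologist's unrecorded impressions.
2. Report nephrologist vetoes with their reasons, and approach and enrolment rates, by arm from the logs already kept, next to baseline eGFR by arm.
3. Reconcile sections 4.1 and 4.2 on who holds the first discussion at Rochester General, and state which was done.
4. For any nephrologist not yet randomised, and in the next trial, have exclusions marked on the patient list before allocation is disclosed.

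Cost: one extra covariate in models with few clusters, and slightly more reporting work. Items 1 and 2 can still be done if recruitment has closed, and item 1 should be fixed before outcomes are compared by arm.
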